6.1.1 EYP-1901 Composition

EYP-1901 intravitreal insert contains vorolanib as the active ingredient and polyvinyl alcohol as an excipient.

The drug delivery system is placed into a one-time-use siliconized needle attached to an applicator delivery system. The drug product is sterilized after packaging and prior to

distribution. In subject, the needle is inserted through the pars plana and the insert is injected into the vitreous.

Two different doses will be administered by delivering multiple inserts on Day 1 ([Table 5–1](#)). [Table 6–1](#) summarizes the characteristics of the two intravitreal doses of EYP-1901.

Table 6–1: Characteristics of the Two Intravitreal Doses of EYP-1901, Study EYP-1901-204

Dose (µg)	Number of Inserts per Single Applicator	Needle Gauge	Insert Length (mm)
2060	2	22	8
3090	3	22	8

6.1.2 EYP-1901/Sham Applicator Packaging

EYP-1901 is packaged at EyePoint Pharmaceuticals. EYP-1901 loaded applicators (and sham applicators) are placed inside a foil chevron pouch and sealed. The sealed foil pouch is then placed inside a Tyvek® chevron pouch. The final pouch is sent for terminal sterilization. Upon completion of sterilization, each pouch is labeled with a “Sterile” label, and then placed into a labeled box.

6.2 Study Drug Administration

6.2.1 EYP-1901 Intravitreal Insert

Each EYP-1901 insert has been designed to deliver vorolanib into the vitreous humor for at least 9 months. EYP-1901 will be administered to the study eye by a single injection through the pars plana using a pre-loaded applicator with a 22-gauge needle.

6.2.2 EYP-1901 Injection Procedure

For a detailed description of the EYP-1901 injection procedure, please refer to the EYP-1901 Instructions for Use (IFU) document.

6.3 Storage and Dispensing of Study Drugs

EYP-1901 must be stored in a secure place and at controlled room temperature (20°C to 25°C/68°F to 77°F) and in the original container to protect the product from light. Temperature excursions between 15°C to 30°C/59°F to 86°F are acceptable.

The Investigator has the overall responsibility of ensuring that EYP-1901 is stored in a safe location with limited-access under the specified storage conditions. Limited responsibility may be delegated to a pharmacy representative; however, this delegation must be documented.

6.4 Drug Accountability

The Investigator is responsible for ensuring adequate accountability of all used and unused EYP-1901. While the Investigator may delegate components of drug accountability tasks to

documented designee(s) (eg, pharmacist or staff designee), the ultimate responsibility for drug control and accountability resides with the Investigator. This includes acknowledgment of receipt of each shipment (quantity and condition), maintenance of subject dispensing records and returned (as required) documentation. Dispensing records will document quantities received from the Sponsor (or designee) and quantities dispensed to subjects, including treatment kit/package number, date dispensed, subject identification number, subject initials, and the initials of the person dispensing drug will be recorded on the drug accountability log.

During study initiation, the study monitor (Clinical Research Associate, CRA) will evaluate and obtain a copy of each site's written standard operating procedure for study drug disposal/destruction or return to ensure that it complies with Sponsor requirements if supplies will not be returned.

An inspection for inventory and accounting purposes, and the assurance of proper storage, will also be conducted during monitoring visits. Any significant accounting or storage discrepancy will be recorded and reported to the Sponsor and a plan for resolution will be documented. After the monitor has checked and verified drug accountability during interim site visits and at the end of the study, any expired, partially-used, and used product should be handled according to the Sponsor's instructions (ie, returned or destroyed).

6.5 Anaphylaxis, Overdose, and Dose Modification

Vorolanib and the inactive ingredients of EYP-1901 are not known to cause hypersensitivity reactions.

Since EYP-1901 is delivered through a pre-loaded applicator, the risk of accidental overdose is minimal. Refer to the current IB for information on potential risks associated with EYP-1901. Dose modification is not applicable since EYP-1901 is for single-delivery only.

Note: Hypersensitivity reactions to iodine and/or fluorescein used during ocular assessments are also possible.

Signs and symptoms of hypersensitivity include:

- Localized or generalized itching
- Facial flushing, generalized flushing
- Shortness of breath, wheezing
- Uneasiness and agitation
- Local edema followed by facial edema
- Light-headedness/dizziness
- Chest tightness
- Tachycardia
- Hypotension
- Rigors (chills)

If anaphylaxis occurs, the subject should be managed according to standard cardiopulmonary resuscitation (CPR) procedures, as necessary. The subject may require the following treatment:

- Epinephrine (adrenaline) to reduce the allergic response
- Oxygen
- Intravenous antihistamines and cortisone to reduce airway inflammation and improve breathing
- A beta-agonist (such as albuterol) to relieve breathing symptoms

6.6 Prior and Concomitant Medications

6.6.1 Prior Medications

Prior medications are defined as all prescription, vaccinations, supplements, herbal therapies, any prohibited medications, and over-the-counter (OTC) medications taken within the 30 days (whether continuing or not) prior to Day 1 with the exception of previous treatments for NPDR, both approved and investigational products. Previous treatments for NPDR are to be captured for the 12 months prior to Screening, and any historical anti-VEGF injections.

All prior medications must be documented on the concomitant medications eCRF.

6.6.2 Concomitant Medications

All prescription and OTC concomitant medications used concurrently (from the Screening Visit to Week 48 or Early Termination) must be documented on the concomitant medication eCRF.

Information on the concomitant medication eCRF includes the name of the medication/therapy, dose, frequency, route, dates of use, and indication for use. Subjects should be instructed not to take any medication including OTC products, without first consulting with the Investigator. Any AE(s) that result(s) from taking a concomitant medication following the first study dose should be recorded on the AE eCRF.

6.6.3 Prohibited Concomitant Medications

Any medications or therapies that the subject is using during the study period and that would preclude eligibility as indicated in the Exclusion Criteria ([Section 4.2](#)), are prohibited concomitant medications. In addition, any medication or therapies initiated during the study period that, in the Investigator's judgment, could potentially confound the safety and preliminary efficacy of EYP-1901 would also be considered prohibited concomitant medications.

All prohibited concomitant medications used concurrently (from Day 1 to Week 48 or Early Termination) must be documented on the concomitant medication eCRF

6.6.4 Permitted Medication and Procedures

Following the intravitreal injections of either dose of the EYP-1901 insert (2060 µg or 3090 µg) on Day 1, treatment of the fellow eye will be at the discretion of the Investigator. Any fellow eye therapy should be documented in concomitant meds during the study if required.

After Day 1, all subjects, regardless of treatment assignment, may receive approved anti-VEGF supplemental therapy or other standard of care therapy if they have ocular diabetic complications

warranting intervention. All ocular diabetic complications in the study eye will be managed in accordance with each study center's standard of care and must be documented as an AE.

During the study, participants who develop ocular diabetic complications in the study eye requiring anti-VEGF treatment per standard of care may be administered therapy as required. If needed, the study centers will provide their own supply of FDA-approved anti-VEGF therapy and submit the associated costs for reimbursement. The number of anti-VEGF injections received, the name of the product being injected, and the timing of all injections must be recorded in the source documents and eCRF.

Participants who develop ocular diabetic complications requiring PRP or retinal laser standard of care must have the time of laser treatment recorded in the source documents and eCRF.

Participants who develop ocular diabetic complications requiring surgical intervention standard of care (eg, pneumatic retinopexy, cryopexy, scleral buckle) must have the type of intervention and the time of intervention recorded in the source documents and eCRF.

In this case, the Investigator is required to contact the Medical Monitor prior to administering treatment if feasible.

7 ASSESSMENT OF SAFETY

Safety assessments will include the incidence and severity of TEAEs reported after Screening, clinical laboratory evaluations (hematology, serum chemistry, coagulation, and urinalysis), safety data collected from ocular examinations and IOP measurements, vital sign measurements, ECGs, and the use of concomitant medications.

Medical safety reviews will be conducted by the Sponsor for all TEAEs and other relevant information related to safety on an ongoing basis and throughout the duration of the study according to the study Safety Management Plan.

7.1 Adverse Events

The following are specific definitions of terms guided by the International Council for Harmonization of Technical Requirements for Pharmaceuticals for Human Use (ICH E2), Guidelines for Good Clinical Practice (GCP), and the US Code of Federal Regulations (CFR) that apply to the following sections. The severity of AEs will be graded by CTCAE version 5 or higher ([Appendix 4](#)).

Definition of Adverse Event:

An AE is defined as any new untoward medical occurrence or worsening of a pre-existing medical condition in a patient or clinical investigation subject administered an investigational or marketed (medicinal) product and that does not necessarily have a causal relationship with the product. An AE can therefore be any unfavorable and unintended sign (including an abnormal laboratory finding, for example), symptom, or disease temporally associated with the use of a medicinal product, whether or not considered related to the product.

AEs may also include pre- or post-treatment complications that occur as a result of protocol-specified procedures (eg, invasive procedures such as venipuncture, delivery procedure, etc.). Pre-existing conditions that increase in severity or change in nature during (or as a consequence of use of a medicinal product) the study will also be considered AEs.

An AE Will Not Include:

- Medical or surgical procedures (eg, surgery, endoscopy, tooth extraction, transfusion) for events that led to the procedure
- Pre-existing diseases, conditions, or laboratory abnormalities present or detected prior to the Screening Visit, unless they worsen during the study
- Situations where an AE or untoward medical occurrence has not occurred (eg, hospitalization for elective surgery, social and/or convenience admissions)

Associated with the Use of the Drug (Causality):

There is a reasonable possibility that the event may have been caused by the study medicinal product (and/or the administration procedures).

Unexpected Adverse Event:

Any event that is not identified in nature, severity, or frequency in the current version of the IB; or in the product labeling for marketed products. For example, if the IB or product labeling referred to elevated hepatic enzymes or hepatitis, then an event of hepatic necrosis would be considered unexpected by the virtue of the greater severity. The Sponsor or designee will determine AE expectedness.

7.1.1 Ocular Adverse Events

The following ocular events will be considered AEs for the purposes of this study:

- Decrease in BCVA of ≥ 15 letters or ≥ 3 lines from the previous BCVA measurement
- Moderate or severe (Grade 2 or 3) ocular findings compared to the last ocular examination
- Worsening of >2 steps in anterior chamber cell count or vitreous haze compared to the last ocular examination
- Increase in IOP of >10 mmHg at two visits at least 1 week apart or an increase in IOP to >25 mmHg

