7.1.2 Serious Adverse Events

An SAE is any AE that results in one of the following outcomes:

- Death.
- Is life-threatening (the term “life-threatening” refers to an event in which the subject was at risk of death at the time of the event; it does not refer to an event which hypothetically might have caused death if it were more intense).
- Requires in-patient hospitalization (formal admission to a hospital for medical reasons for any length of time), or prolongs existing hospitalization.
- Results in a persistent or significant disability/incapacity, or substantial disruption of the ability to conduct normal life functions.

- Congenital anomaly/birth defect (in the child of a subject who was exposed to the study treatment).
- Other important medical event. Medical and scientific judgment should be exercised in determining whether an event is an important medical event. An important medical event may not be immediately life-threatening and/or result in death or hospitalization but required medical intervention in order to prevent a SAE outcome. However, if it is determined that the event may jeopardize the subject and/or may require intervention to prevent one of the other SAE outcomes, the important medical event should be reported as serious. Examples of such events are intensive treatment in an emergency room or at home for allergic bronchospasm; blood dyscrasias or convulsions that do not result in hospitalization; or development of drug dependency or drug abuse.

The following hospitalizations will not be considered SAEs:

- A visit to the emergency room or other hospital department for <24 hours that does not result in in-patient admission (unless considered an “important medical event” or a “life -threatening event”).
- Elective surgery or planned surgery prior to signing the ICF.
- Admissions as per protocol for a planned medical/surgical procedure.
- Routine health assessments requiring admission for Baseline/trending of health status (eg, routine colonoscopy).
- Medical/surgical admission for a purpose other than healthcare purposes and was planned prior to entry into the study (appropriate documentation is required in these cases).
- Admission encountered for another life circumstance that carries no bearing on health status and/or requires no medical/surgical intervention (eg, lack of housing, economic inadequacy, care-giver respite, family circumstances, administrative).

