7.1.3 Sight-Threatening Ocular Events Defined as SAEs in This Study

In addition to the standard SAE categories described above, this study defines these additional ocular events as SAEs:

- An AE that causes a decrease in visual acuity of ≥ 30 letters or ≥ 6 lines from the most recent previous measurement of visual acuity, lasting more than 1 hour.
- An AE that causes a decrease in visual acuity to light perception or worse, lasting more than 1 hour.
- An AE that requires surgical intervention (eg, conventional surgery, vitreous tap, or biopsy with intravitreal injection of anti-infectives, or laser or retinal cryopexy with gas) to prevent permanent loss of sight.
- An AE that is associated with severe intraocular inflammation (ie, 4+ anterior chamber cell score or 4+ vitreous haze score).
- Two consecutive IOP measurements of ≥ 30 mmHg taken at least 72 hours apart when a subject is already being treated with two IOP-lowering medications.
- An IOP < 6 mmHg requiring medical intervention.
- An AE that in the opinion of the Investigator requires medical or surgical intervention to prevent permanent loss of sight.

The Investigator must employ all necessary therapeutic measures to resolve the SAE. Any medications or therapies used to treat the SAE must be recorded in the concomitant medication eCRF.

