### **11.7. Best Corrected Visual Acuity**

Observed BCVA values and change from baseline to each follow-up visit are to be summarized descriptively (n, mean, SD, median, min, and max) for the FAS (identical to the Safety Set) by treatment arm and overall for the study eye and non-study eye as part of the efficacy analysis ([Section 10.2](#)).

The following endpoints will be summarized descriptively for the Safety Set by treatment arm and overall for the study eye using counts and percentages of participants at each scheduled visit and a corresponding 95% Clopper-Pearson CI for proportion with response by treatment group. The difference in the proportion of subjects with the desired response will be presented for each active treatment arm minus sham IVT, and the corresponding 95% Chan-Zhang CI presented.

- Proportion of subjects with ≥5 BCVA letter loss
- Proportion of subjects with ≥5 BCVA letter gain

*This document is confidential.*

- Proportion of subjects with  $\geq 10$  BCVA letter loss
- Proportion of subjects with  $\geq 10$  BCVA letter gain
- Proportion of subjects with  $\geq 15$  BCVA letter loss
- Proportion of subjects with  $\geq 15$  BCVA letter gain

This document is confidential.

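### The 15-letter AE rule and the 30-letter SAE rule use only the preceding reading, so a cumulative loss of 30 or more letters in steps under 15 meets neither

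*Protocol*

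**What the plan says.** Protocol 7.1.1 lists events that are to be treated as ocular AEs. One is a fall in BCVA of at least 15 letters, or at least three "lines from the previous BCVA measurement".

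Protocol 7.1.3 adds sight-threatening events that count as SAEs. One is an AE causing a "decrease in visual acuity of ≥ 30 letters or ≥ 6 lines from the most recent previous measurement of visual acuity" that lasts more than an hour. Two other limbs of 7.1.3 use no earlier reading: an AE-caused "decrease in visual acuity to light perception or worse, lasting more than 1 hour", and an AE that in the Investigator's opinion "requires medical or surgical intervention to prevent permanent loss of sight". The general SAE list in 7.1.2 includes an AE that "Results in a persistent or significant disability/incapacity".

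Other sections also bear on gradual loss:

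- Protocol 7.1 counts any new untoward occurrence, or worsening of an existing condition, as an AE.
- Protocol 6.6.4 requires ocular diabetic complications in the study eye to be documented as AEs.
- Protocol 7.1.2 has progressive disease recorded as an AE, but excludes NPDR progression from SAEs.
- Protocol 7.1.4 makes a laboratory abnormality an AE if its severity rises relative to baseline.

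SAP 11.7 works from baseline: "Observed BCVA values and change from baseline to each follow-up visit are to be summarized descriptively". It also tabulates the proportions of subjects losing at least 5, 10 and 15 letters in the study eye at each scheduled visit. Listing 16.2.6.2.3 gives change from baseline, gains and losses by subject.

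**The concern.** BCVA is measured at every scheduled visit, so the reference for both letter rules moves down with the eye. A slow decline can add up to a large loss without any single step reaching a threshold. Release is expected to last at least 9 months and follow-up runs to Week 48, so gradual loss is a pattern that the safety rules should handle clearly.

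The purpose of a numeric trigger is to make reporting uniform. Where it is silent, one site may record an AE for a 20-letter cumulative loss and another may not. The same subject can then appear in the SAP table of losses of 15 letters or more with no letter-rule AE having been required. In arms of about 20, one subject is 1/20 = 5 percentage points.

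**Working it through.** The documents give no figure on this point to reproduce. The check applies the two rules as written.

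**Inputs**
- AE threshold 15 letters, previous-reading reference (Protocol 7.1.1).
- SAE threshold 30 letters, most recent previous reading (Protocol 7.1.3).
- Post-dose visits at Weeks 4, 12, 24, 36 and 48 (Protocol Table 5-1), giving 5 intervals from Day 1.
- Minimum entry BCVA 69 letters (Protocol 4.1).
- Letters per line: 15/3 = 5 and 30/6 = 5, so the letter and line limbs coincide.

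**Largest loss that never meets the AE letter rule**

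Intervals × (threshold − 1) = 5 × 14 = 70 letters. This is an arithmetic ceiling and not an expected course. It exceeds the whole score of an eye entering at 69.

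**Fewest visits to lose 30 letters with every step at 14 or less**

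30/14 = 2.14, so 3 visits (for example 14 + 14 + 2).

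**Example paths from 69 letters at Day 1**

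Each cell shows the first visit at which the 15-letter / 30-letter threshold is met. The last column keeps the same thresholds but measures from baseline.

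| Drops at Weeks 4, 12, 24, 36, 48 | Previous-reading reference | Baseline reference |
|---|---|---|
| 6, 6, 6, 6, 6 | none / none | Week 24 / Week 48 |
| 10, 10, 10, 0, 0 | none / none | Week 12 / Week 24 |
| 14, 14, 14, 14, 13 | none / none | Week 12 / Week 24 |
| 15, 15, 0, 0, 0 | Week 4 / none | Week 4 / Week 12 |
| 0, 0, 16, 14, 0 | Week 24 / none | Week 24 / Week 36 |
| 30, 0, 0, 0, 0 | Week 4 / Week 4 | Week 4 / Week 4 |

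The first three rows meet neither letter rule. The fourth and fifth meet the AE rule but miss the 30-letter SAE rule.

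**How general the gap is**

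There are 46,376 ways to lose exactly 30 whole letters over 5 intervals with no gains. Of these, 27,006 (58.2%) have every step below 15 and so miss the AE rule. All but the 5 single-visit drops, that is 46,371, miss the 30-letter rule. These count possible paths and are not probabilities.

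**The same subject in two tables**

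On the 10, 10, 10 path, the loss from baseline is 10 letters at Week 4, 20 at Week 12 and 30 at Week 24. SAP 11.7 counts this subject among losses of at least 15 letters from Week 12. Protocol 7.1.1 has required no AE by its letter rule at any of these visits.

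**The case against.** The strongest reply is that 7.1.1 and 7.1.3 add to the general definitions and do not replace them. Sections 6.6.4, 7.1 and 7.1.2 already make diabetic complications, worsening conditions and progression recordable as AEs whatever the letter step. SAP 11.7 shows baseline-referenced loss by arm and the listing shows it by subject. The neighbouring bullets in 7.1.1 also compare ocular findings, cells and haze with the last examination, so the set can be read as a coherent screen for acute change.

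Much of this stands, and it rules out several stronger readings that a reader might infer:

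- **Any stepwise loss of 30 letters escapes both rules.** It does not. 15 + 15 meets the AE rule at the first drop, and 20 + 20 meets it at both; each misses only the 30-letter SAE limb.
- **Ocular TEAE and SAE rates are understated.** The documents do not show this, because other routes to reporting exist. For NPDR progression, leaving it out of SAEs is a stated decision in 7.1.2.
- **The Sponsor would not see the loss.** Protocol 7 extends safety review beyond TEAEs to other relevant safety information, under a Safety Management Plan that is not among the documents.
- **The most closely watched eye is the least likely to qualify.** The minimum set for unscheduled visits is photography, SD-OCT and angiography. BCVA is not in it.

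The acute-change reading fits 7.1.3 better than 7.1.1. Only 7.1.3 carries the one-hour duration, whereas after Week 4 the AE rule compares scheduled readings 8 or 12 weeks apart. The other routes also leave recording to site judgement, and they supply no letter rule measured from baseline.

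**Conclusion.** The point holds for the two letter-count rules. A cumulative loss of 30 or more letters in which every between-visit step is under 15 meets neither, and no letter rule measured from baseline exists. Such a loss can still be recorded by other routes, so the consequence is uneven AE capture between sites and AE tables that may not match the BCVA-loss tables. How often this would happen cannot be estimated from the documents.

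The case is firm for the AE rule. It is more open for the 30-letter SAE rule, which may be meant for acute loss and interacts with the exclusion of NPDR progression from SAEs.

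Assumptions: previous means the immediately preceding measurement (7.1.3 says so, 7.1.1 does not spell it out); five letters to a line; no BCVA readings between scheduled visits; and the SAP's letter-loss categories are measured from baseline, as the context in SAP 11.7 and the listing title indicate.

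**What to change.** 1. In Protocol 7.1.1, keep the 15-letter threshold but apply it to the loss from baseline (as defined in SAP 8.2) or from the previous measurement, whichever is larger. The previous-reading limb still catches an eye that first gains and then falls. State that the first crossing counts, so that a persisting loss is not reported again at each visit.
2. Add an eCRF edit check that queries the site when the loss from baseline reaches 15 letters and no AE is on file. Alternatively, reconcile Listing 16.2.6.2.3 against reported AEs to the same end. A recorded diagnosis that accounts for the loss would close the query.
3. In Protocol 7.1.3, state whether cumulative loss is meant to count towards the 30-letter rule, and reconcile the answer with the exclusion of NPDR progression from SAEs in 7.1.2.

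The cost is a phrase in 7.1.1, a clarification in 7.1.3 and one check on data already collected at every scheduled visit. No new assessment is needed. The downside is somewhat more ocular AE queries and reports.
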